#### **6.4.4 Week 52 (Visit 9)**

Subjects will be instructed to come into the study center after having fasted for approximately 6 to 8 hours and prior to taking their study medication. Appointments should be scheduled accordingly to accommodate this fasting status (ie, in the morning). The following procedures will be performed:

- Record any change in concomitant medications on the appropriate concomitant medication eCRF, including dose and frequency.
- Adverse event evaluation/update, including any incidences of hypocalcemia or hypercalcemia
- Vital signs measurements (prior to blood draws) and weight

- Physical examination
- 12-lead electrocardiogram
- Blood samples for serum chemistries (including calcium, phosphate, albumin, and magnesium), hematology, serum 25(OH) vitamin D, serum 1,25-dihydroxyvitamin D, creatinine clearance, and bone turnover markers
- Blood sample for PTH and ECP antibodies (predose) (See Section 6.2 for additional follow-up for subjects who develop antibodies specific to PTH.)
- Urinalysis
- 24-hour urine calcium, phosphate, sodium, and creatinine
- A BMD test by DXA
- Serum  $\beta$ -HCG pregnancy test (WOCBP only)
- Review the subject's diary to assess compliance to protocol procedures and dosing/supplement regimens.
- Collect used and unused drug cartridges and supplements (calcium and calcitriol) for assessment of accountability.
- Subjects will be provided with the following study supplies:
  - Study medication cartridges in sufficient number to supply daily doses until the next scheduled clinic visit
  - Calcium (carbonate or citrate) supplements in sufficient quantity to supply daily doses until the next scheduled clinic visit
  - Ancillary injection supplies (ie, alcohol swabs, needles, etc.)
  - Paper diaries
  - Collection container for 24-hour urine

#### **6.4.5 Long-term Extension Visits**

Subjects who continue into the long-term extension will have the following evaluations performed every 2 months unless otherwise indicated:

- Record any change in concomitant medications on the appropriate concomitant medication eCRF, including dose and frequency.
- Adverse event evaluation/update, including any incidences of hypocalcemia or hypercalcemia
- Urine pregnancy test (WOCBP only)
- Brief physical examination (every 6 months)
- Vital signs measurements (prior to blood draws) and weight
- Blood samples for serum chemistries and hematology (every 12 months)
- Blood samples for creatinine clearance and bone turnover markers (every 4 months)
- Local total serum calcium (as needed)
- Blood sample for PTH and ECP antibodies (predose) (every 6 months)
- Serum calcium and phosphate

- Serum 25(OH) vitamin D
- Serum 1,25-dihydroxyvitamin D (every 6 months)
- 24-hour urine calcium, phosphate, sodium, and creatinine (every 4 months)
- A BMD test by DXA (every 12 months)
- If calcium-sparing diuretics are instituted and/or the dose subsequently changed, monitoring for serum potassium, sodium, and calcium will be done 1 week and again 1 month later and then at each subsequent scheduled clinic visit.
- Review the subject's diary to assess compliance to protocol procedures and dosing/supplement regimens. Subjects will complete the diary for the 2-week period prior to the scheduled study visit. If the subject does not record the diary information as indicated during this time period, he/she may record it during the 2 weeks following the visit. This information will then be reviewed with the subject by phone or at the next scheduled visit.
- Collect used and unused drug cartridges and pen injectors for assessment of accountability.
- Subjects will be provided with the following study supplies:
  - Study medication cartridges in sufficient number to supply daily doses until the next scheduled clinic visit
  - Ancillary injection supplies (ie, alcohol swabs, needles, etc.)
  - Calcium (carbonate or citrate) supplements in sufficient quantity to supply daily doses until the next scheduled clinic visit through approximately May 2014. Following this date, only calcium citrate will be provided.
  - Collection container for 24-hour urine

#### **6.4.6 End of Treatment Visit or Early Termination**

- Record any change in concomitant medications on the appropriate concomitant medication eCRF, including dose and frequency.
- Adverse event evaluation/update, including any incidences of hypocalcemia or hypercalcemia
- Full physical examination
- Vital signs measurements (prior to blood draws) and weight
- 12-lead ECG (may be local)
- A BMD test by DXA (if previous DXA was  $\geq 3$  months prior)
- Blood samples for serum chemistries (including calcium and phosphate), hematology, serum 25(OH) vitamin D, serum 1,25-dihydroxyvitamin D, creatinine clearance, and bone turnover markers
- Blood sample for PTH and ECP antibodies (See Section 6.2 for additional follow-up for subjects who develop antibodies specific to PTH.)
- Administration of the last dose of study medication following the predose PTH samples
- Urinalysis
- 24-hour urine calcium, phosphate, sodium, and creatinine
- Serum  $\beta$ -HCG pregnancy test (WOCBP only)

- Review the subject's diary
- Collect used and unused drug cartridges and pen injectors, for assessment of accountability, and subject diaries.
- Subjects will either be prescribed appropriate oral calcium and/or active vitamin D to compensate for the cessation of NPSP558 (rhPTH[1-84]) or may opt to continue treatment on commercial drug (Natpara). Subjects who continue treatment with Natpara will continue to be monitored under the care of a physician according to approved labeling instructions.

#### **6.4.7 Posttreatment Serum Calcium/Phosphate Follow Up**

After the End of Treatment visit or early termination visit, subjects who will not continue rhPTH[1-84] treatment will have their total serum calcium and phosphate levels measured 3 to 5 days after the last dose of study medication. Doses of calcium and active vitamin D supplements will be adjusted by the Investigator as appropriate. Thereafter, the Investigator will repeat serum calcium/phosphate monitoring and supplement dose adjustments as appropriate to achieve target serum calcium/phosphate concentrations until the follow up phone call 4 weeks  $\pm$  7 days after end of treatment visit. After the 4-weeks follow-up telephone call, further management of hypoparathyroidism will occur as part of the subject's long-term non-study medical care.

#### **6.4.8 Follow-up Telephone Contact**

Subjects will be contacted approximately 4 weeks following the last dose of study medication to monitor for and/or follow-up on any study drug-related AE or any SAE that may have occurred during the study period or any SAE that may have occurred since the last study drug injection.

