#### **6.2.1.3 Procedures for Reporting Adverse Events**

Adverse events may be spontaneously reported by the subject, obtained through nonleading questioning, or noted during examination of a subject. All AEs and SAEs will be recorded from the signing of the ICF through the last study visit or the last study required procedure (including the follow-up telephone call 4 weeks after end of treatment). SAEs will be monitored with a telephone call by the investigator, as necessary, for approximately 4 weeks after the last dose of study drug, or until resolution or the SAE is judged by the investigator to have stabilized.

The AE term should note the diagnosis whenever possible, not the individual signs or symptoms (eg, myocardial infarction should be recorded rather than chest pain, elevated cardiac enzymes, and abnormal ECG). Also recorded are:

- Start and stop date and time
- Whether the event is continuing
- Frequency (intermittent, continuous)
- Intensity (mild, moderate, severe)
  - Mild: usually transient, requiring no special treatment and generally not interfering with usual daily activities
  - Moderate: usually ameliorated by simple therapeutic maneuvers and impairs usual activities
  - Severe: requires vigorous therapeutic intervention and interrupts usual activities. Hospitalization may or may not be required.

- Relationship to study drug (not related, related): identify relationship as “related” if a causal relationship between the investigational product and an AE is at least a reasonable possibility (ie, the relationship cannot be ruled out)
- Whether the AE is serious (ie, an SAE). If identified as an SAE, the AE should be reported on the SAE form according to Section 6.2.2.2 below.
- Actions taken (none; study drug dose changed, interrupted, or discontinued; other medication change; nondrug therapy)
- Outcome (resolved, resolved with sequelae, ongoing, fatal). An individual AE receives only one outcome.

Adverse events that are related to study drug and that have not resolved at the end of treatment will be followed by the site until resolution or until the AE is judged by the investigator to have stabilized.

Laboratory values, blood pressure, ECG evaluations, and clinical findings at the scheduled physical examinations must be reported as AEs if they:

- Are considered clinically significant by the investigator
- Fulfill SAE criteria, and/or
- Cause subject discontinuation from the study.

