**Table 6-3 Schedule of Evaluations and Procedures – Long-term Extension after Month 36**

Study Procedures	Proposed Study Month a	Months 38/50/62	Months 40/52/64	Months 42/54/66/74	Months 44/56/68/76	Months 46/58/70/78	Months 48/60/72/80	End of Treatment b	4 weeks F/up Phone c
	Visit Windows	± 2 weeks	± 2 weeks	± 2 weeks	± 2 weeks	± 2 weeks	± 2 weeks	± 1 week	± 7 days

a Study visits will be conducted every 2 months and will continue until the subject voluntarily withdraws or until termination of the study. At that time, and periodically following that milestone, the study will be reviewed in regard to continuation/termination status.

b After the End of Treatment visit or early termination visit, subjects who will not continue rhPTH[1-84] treatment will have their total serum calcium and phosphate levels measured 3 to 5 days after the last dose of study medication. Doses of calcium and active vitamin D supplements will be adjusted by the Investigator as appropriate. Thereafter, the Investigator will repeat serum calcium/phosphate monitoring and supplement dose adjustments as appropriate to achieve target serum calcium/phosphate concentrations until the follow up phone call 4 weeks ± 7 days after end of treatment visit. After the 4 week follow up phone call, further management of hypoparathyroidism will occur as part of the subject's long-term non-study medical care.

c Follow-up phone contact 4 weeks after the last dose of study medication to check on any ongoing or new drug-related AEs or SAEs

d Study subjects must be re-consented at their next study visit prior to implementation of Amendment 6.

e Brief physical exams will be conducted at 6-month intervals.

f Vital signs should be done prior to blood draws.

g The End of Treatment ECG will be read locally.

h Calcium supplements should be withheld for 24 hours prior to the DXA scan. If a subject cannot withhold the calcium supplements due to safety concern, the DXA should be performed 2 hours after the last calcium tablet has been ingested.

i DXA will be performed at End of Treatment visit ONLY if the previous DXA was ≥3 months prior.

j Fasting for at least 6 to 8 hours prior to test

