6.8.1. Adverse Events

Adverse events will be coded using MedDRA Version 13.0. Adverse event listings will provide the verbatim term as well as SOC and PT for each recorded event. A separate listing may be produced to provide the SOC, high level term, PT, and lower level term that are associated with each verbatim term.

Treatment emergent adverse events (TEAEs) are defined as AEs whose onset occurs, severity worsens or intensity increases after receiving the study medication of this study and ≤ 30 days after last dose of study drug. If any AE records contain only partial dates, these will be handled by imputation, as described in Section 7.4.3. AEs which are not treatment emergent will be flagged in listings.

An overview of TEAEs will be summarized using the number and percentage of subjects. The number of events will also be presented except for summaries by highest category. Categories summarized will include any TEAEs, severity of TEAEs (any and highest category), relationship of TEAEs to treatment (any and highest category), treatment emergent serious AEs (TESAEs), severity of TESAEs, relationship of TESAEs to treatment, TEAEs leading to discontinuation, and TEAEs leading to death.

Treatment emergent AEs will be summarized using number and percentage of subjects. Subject incidence for AEs within each SOC and PT will be presented, and the number of events will also be summarized except for summaries by highest category. Categories summarized will be the same as those summarized overall, except that no summary table will be provided for TEAEs leading to death.

Summaries of TEAEs and TESAEs will also be presented by PT. These presentations will be sorted by descending incidence.

Listings will be provided for serious adverse events (SAEs), AEs leading to discontinuation, and AEs leading to deaths.

The incidence of hypocalcemia and hypercalcemia will be identified by clinical preview. Prevalence of hypocalcemia and hypercalcemia will be assessed at all visits on the date of visit. The number of subjects with hypocalcemia and hypercalcemia and the number of episodes of hypocalcemia and hypercalcemia will be assessed for the overall trial.

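### The protocol gives the 4-week follow-up call two different scopes for adverse events, and the narrower one, with a window opening at Day 21, does not match the SAP's 30-day treatment-emergent rule

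*Protocol*

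**What the plan says.** The protocol describes the same call in two ways.

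- **Restricted scope.** Section 6.4.8 directs the call at "any study drug-related AE or any SAE that may have occurred during the study period", and then at any SAE since the last injection. For the time after the last injection it therefore names SAEs only. Footnote c of Table 6-3 says the contact is "to check on any ongoing or new drug-related AEs or SAEs". The SAP repeats that footnote under its Table 4.3.
- **All AEs.** Section 6.2.1.3 states that "All AEs and SAEs will be recorded from the signing of the ICF through the last study visit or the last study required procedure", and adds that this includes the 4-week call. Section 3.1 and the note to Figure 3-2 have subjects telephoned about 4 weeks (glossed as 30 days) after the End of Treatment visit to assess AEs and SAEs, with no relatedness limit. The adverse event row of Table 6-3 is also marked at the call, although footnote c sits on that column.

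Timing varies too. Section 6.4.8 counts from the last dose: "Subjects will be contacted approximately 4 weeks following the last dose of study medication". Section 6.4.7 places the call 4 weeks ± 7 days from the End of Treatment visit, and Table 6-3 also gives ± 7 days.

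On the analysis side, SAP Section 6.8.1 treats an AE as treatment emergent if it starts or worsens after the first dose in this study and "≤ 30 days after last dose of study drug". Relationship plays no part in that definition.

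**The concern.** The primary objective is long-term safety and tolerability, and the SAP tabulates treatment-emergent AEs overall and by relationship. If the call is run from the restricted text, non-serious events that the investigator regards as unrelated are not asked about, yet the analysis counts them. On a literal reading of Section 6.4.8, even related non-serious events that begin after the last injection fall outside the call, although footnote c would include them.

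Ascertainment after the last dose would then depend on a causality judgement made in an open-label study, and the by-relationship table would inherit that filter. Missing safety data are not imputed (SAP Section 5.4.2) and summaries use observed values (SAP Section 6.8), so an event nobody asked about appears as no event. Sites may also differ, depending on which section they follow.

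**Working it through.** **Scope.** The sources give these answers to whether a non-serious AE, judged unrelated and starting after the last dose, is covered:

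| Source | Covered? |
|---|---|
| Protocol 3.1 and Figure 3-2 note | Yes, assessed at the call |
| Protocol 6.2.1.3 | Yes, recorded through the call |
| Protocol 6.4.8 | No |
| Protocol Table 6-3 footnote c; SAP Table 4.3 footnote c | No |
| SAP 6.8.1 | Yes, counted if within 30 days of last dose |

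The first and last rows cannot both be met by a call run from the two middle sources.

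**Timing.** Inputs: nominal call at 4 weeks = 28 days; window ± 7 days (Section 6.4.7, Table 6-3); treatment-emergent limit 30 days after last dose (SAP Section 6.8.1). Section 6.4.6 lists "Administration of the last dose of study medication following the predose PTH samples" at the End of Treatment visit, so the two anchors coincide for subjects dosed there.

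- Earliest call: 28 − 7 = Day 21. Latest: 28 + 7 = Day 35.
- Days of the post-dose period left after the call = max(0, 30 − call day).

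| Call day | Days left | Share of 30 post-dose days |
|---|---|---|
| 21 | 30 − 21 = 9 | 9/30 = 30.0% |
| 28 | 30 − 28 = 2 | 2/30 = 6.7% |
| 30 to 35 | 0 | 0% |

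Of the 15 permitted call days (21 to 35), 9 fall before Day 30 (21 to 29).

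**Anchor.** If dosing stopped k days before the End of Treatment visit and the call is timed from the visit, the earliest call is Day 21 + k after the last dose and the gap is max(0, 9 − k). It shrinks as k grows.

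**Denominator.** The 30% refers only to the post-dose tail. The treatment-emergent window begins at the first dose. With 52 weeks of treatment it is 364 + 30 = 394 days, and 9/394 = 2.3%. With the 80 months in Section 3.2, taking 30.44 days per month, it is about 2,435 + 30 = 2,465 days, and 9/2,465 = 0.4%.

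**The case against.** Section 6.2.1.3 is the section that governs AE recording, and it requires all AEs through the call. A site that follows it records whatever a subject reports, so the restricted wording could be seen as loose drafting. Subjects who stop the drug also have other contacts: calcium and phosphate measured 3 to 5 days after the last dose, a clinic visit at the end of that week (Section 3.1), and repeat monitoring as appropriate until the call (Section 6.4.7). Subjects who move to commercial drug have a one-week wellness check. SAEs are reportable for 30 days whatever the call date (Sections 6.2.2 and 6.2.2.2), and Table 6-4 adds AE assessment at Months 3 and 6 for certain antibody-positive subjects. Related is defined broadly in Section 6.2.1.3, so much post-treatment hypocalcaemia might be classed as related. The SAP's 30 days is a classification limit and promises no contact on Day 30.

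Most of this stands, and it limits the effect. It does not remove the conflict. A duty to record is not an instruction to ask, and the text describing the call itself gives the narrower instruction. The documents do not schedule AE questioning at the calcium checks. No contact is planned for most subjects after an early call, so even SAEs between then and Day 30 depend on the site hearing of them.

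A reader might infer three stronger things that the documents do not support:

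- That unrelated non-serious AEs after the last dose go uncollected. Sections 3.1 and 6.2.1.3 say otherwise, and other contacts exist.
- That 30% of the treatment-emergent window is unobserved. The figure covers only the 30-day tail at the earliest permitted call.
- That calcium control is most at risk in these weeks. The post-treatment monitoring shows that the protocol takes the period seriously, but no passage makes that comparison.

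**Conclusion.** The inconsistency is real in current text and should be corrected. Section 6.4.8 and footnote c of Table 6-3 conflict with Sections 3.1 and 6.2.1.3 and the Figure 3-2 note, and they supply less than SAP Section 6.8.1 counts. The consequence is possible under-ascertainment of post-dose treatment-emergent AEs, filtered by causality judgement and confined mainly to non-serious events judged unrelated. Its size cannot be calculated, because the documents give neither post-dose event rates nor which text sites follow.

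The timing gap is secondary: at most 9 days, 2 at the nominal call and none from Day 30. This assumes that the last dose is given at the End of Treatment visit and that the subject has no later antibody follow-up.

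**What to change.** 1. Reword Section 6.4.8 and footnote c of Table 6-3, and its copy under SAP Table 4.3, so that the call asks about all AEs and SAEs regardless of relationship.
2. Use one anchor, the last dose, and place the call on or after Day 30, for example Day 30 to 35. The days left after the call are then zero.
3. Carry the change to every place where 4 weeks ± 7 days appears: the Synopsis, Section 6.4.7, the footnotes to Tables 6-1 and 6-2, the column and footnotes of Table 6-3, and in the SAP Section 3.1 and Tables 4.1 to 4.3. Align Sections 3.1 and 6.2.1.3 and the Figure 3-2 note to the same anchor.

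Section 6.4.7 also uses the call to mark the end of post-treatment calcium and phosphate monitoring. Moving the call moves that end point unless the two are separated. The sponsor should state which is intended.

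The cost is a slightly longer call and several consequential wording edits. The analysis definition does not change.

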#### **6.4.9 Follow-up assessment for PTH antibodies**

Any subject who tests positive for PTH-specific antibodies at the last 2 consecutive visits at which antibodies are measured and does NOT continue treatment on commercial Natpara, will have follow-up blood draws for PTH antibodies at Months 3 and 6 poststudy. If a subject's results are negative at Month 3, follow-up may be terminated.

### **7 DATA MANAGEMENT**

#### **7.1 Data Collection**

Data collected during the study will be recorded in the subject's eCRF by the study center's research team. The research team will keep records of the subject's visit in the files considered as source documents for that center, eg, hospital chart, research chart, etc. To ensure that data have been entered correctly on the eCRF, eCRFs will be 100% source-data verified by a monitor from the sponsor/designee, who will notify the investigator regarding questions or missing data. The investigator or designee will be responsible for the timely recording of subject data.

The investigator will review all eCRFs (including the termination page after the subject's final visit) for completeness and accuracy, and will electronically sign the eCRFs attesting to this prior to submitting them to the sponsor. The investigator will be responsible for submitting the data to

the sponsor (or designee) in a timely manner, on the eCRFs provided by the sponsor (or designee) for this purpose. Non-CRF data including, but not limited to central laboratory tests, ECG, and radiographic (DXA) results will be sent to the sponsor or designee via a data transfer from the appropriate vendor for assimilation into the database. SAE reporting must be done within the times described in Section 6.2.2.2.

All data collected in this study will be integrated into an appropriate preformatted database by the sponsor or designee for subsequent statistical evaluation. Data validation and edit checks will be conducted on the data. Any discrepancies will be noted and queries will be generated by the sponsor or designee to be resolved by the center. Queries should be completed by the investigational center and signed by the investigator or approved designee in a timely manner.

When all subjects' data have been entered into the database, verified, and all outstanding issues have been resolved with the center, the data will be evaluated for quality purposes. A clean file is defined as when the data in the database and the reference values are complete and logical according to the clinical study protocol, general guidelines, data management plan, and data entry instructions. Once the sponsor acknowledges that all data are acceptable, the data will be declared to represent a "clean file" and the database will be frozen.

A quality assurance audit will be performed on the data by the Data Management group. When all issues from the audit are resolved, and all data management processes are completed for finalizing the database, the database will be locked and ready for analysis.

The investigator and clinical center must permit study-related monitoring, audits, IRB/IEC/REB review, and regulatory inspections by providing direct access to source data/documents.

Subjects will retain the subject number utilized in the RELAY/REPLACE study. The first four digits consist of the center number and the last four digits are the sequential subject number. This number is the main identifier for subjects.

